3.2. Study population

3.2.1. Inclusion criteria

- Older than 18 years of age and able to give informed consent
- Clinical diagnosis of ADHF within the previous 8 h
- At least two clinical signs of congestion (e.g. edema, ascites, jugular venous distension or pulmonary vascular congestion on chest radiography)
- Maintenance therapy with oral loop diuretics at a dose of at least 1 mg bumetanide or an equivalent dose for at least 1 month before hospital admission
Conversion: 1 mg bumetanide = 40 mg furosemide = 20 mg torsemide
- Plasma NT-proBNP >1,000 pg/mL
- Left ventricular ejection fraction <50% (on examination ≤3 months)
- One out of three of the following criteria:
 - Serum sodium <136 meq/L

- Urea/creatinine ratio >50
- WRF defined as a >0.3 mg/dL increase in Cr compared to a previous value within 3 months before admission

3.2.2. Exclusion criteria

- History of a cardiac transplantation and/or ventricular assist device
- Concurrent diagnosis of an acute coronary syndrome defined as typical chest pain and/or electrocardiographic changes in addition to a troponine rise >99th percentile
- Systolic blood pressure <90 mmHg or mean arterial pressure <65 mmHg at the moment of admission
- Use of intravenous inotropes, vasopressors or nitroprusside at any time point during the study
- A baseline estimated glomerular filtration rate <15 mL/min/1.73m² according to the Chronic Kidney Disease Epidemiology Collaboration (CKD-EPI) formula
- Use of renal replacement therapy or ultrafiltration before study inclusion
- Treatment with acetazolamide during the previous month
- Treatment with ≥2 mg bumetanide or an equivalent dose of loop diuretics during the index hospitalization before randomization
- Use of diuretics or MRA not specified by the protocol
- Exposure to nephrotoxic agents (i.e. contrast dye) anticipated within 3 days

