3.1. Study design

Randomized clinical trial with factorial 2x2 design, 2 treatment arms, and 4 groups (n=20 each):

- Arm 1: Acetazolamide + low-dose loop diuretics versus high-dose loop diuretics (=standard of care)
 - ➔ Triple blinded to treatment allocation (patient, treating physician and investigator blinded)
- Arm 2: Upfront versus discharge spironolactone
 - ➔ Treating physician and investigator blinded to treatment allocation. Patient not blinded to treatment allocation because no matching placebo will be provided due to logistic constraints.

Consecutive patients, presenting with ADHF at different Belgian hospitals will be screened by staff members, cardiology fellows, a study nurse and the cardiology Ph.D. fellows. All those people will be able to login via the website www.hartcentrumlimburg.be, where they can print the case report form and informed consent of the study and will receive the randomization number by a computer algorithm with blocks of 4.

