3.4. Collected data

- Baseline at the moment of randomization
 - Demographics, medical history, current medical therapy, baseline body weight, blood pressure, heart rhythm (sinus or not), heart rate, Visual-analogue scale (VAS) score for dyspnea and 4-point Likert scale for edema will be assessed upon study inclusion
 - Blood sample: hematocrit, electrolytes, serum osmolality, serum urea, serum creatinine, serum Cystatin C, serum urate, plasma renin activity (PRA), plasma aldosterone, plasma adrenaline, plasma noradrenaline, total protein, plasma NT-proBNP
- Day 1-3:
 - VAS score for dyspnea
 - 4-point Likert scale for edema
 - Body weight and fluid balance
 - Blood pressure, heart rate, heart rhythm
 - Blood sample: hematocrit, electrolytes, serum osmolality, serum urea, serum creatinine, serum Cystatin C, serum urate, PRA, plasma aldosterone, plasma adrenaline, plasma noradrenaline, total protein, plasma NT-proBNP
- Three consecutive 24h urinary collections will be performed; the first one started with the first bolus administration of loop diuretics; urinary assessment of creatinine, protein, sodium, potassium, chloride, ureum, urate, microalbuminuria
- At an outpatient follow-up appointment 2-6 weeks after hospital discharge, a final blood sample with hematocrit, electrolytes, serum osmolality serum urea, serum creatinine, serum Cystatin C, serum urate and plasma NT-proBNP will be collected.
- All-cause mortality and hospital readmissions will be collected prospectively for the study cohort. The patient will receive a telephone call from a study nurse after 3, 6, 9 and 12 months

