3.5. Study end-points

3.5.1. Primary study end-point acetazolamide arm

Total urinary sodium excretion (mmol) after 24 h

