3.5.2. Primary study end-point for spironolactone arm

Incidence of hypo- (serum potassium <3.5mmol/L or need for oral/intravenous potassium supplements) or hyperkalemia (serum potassium >5.0mmol/L) during the entire 72 h interval after randomization.

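### The exclusion for intravenous inotropes, vasopressors or nitroprusside runs past randomisation, and no analysis set keeps such patients in

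*Combined protocol and SAP*

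**What the plan says.** Section 3.2.2 excludes patients for "Use of intravenous inotropes, vasopressors or nitroprusside at any time point during the study". Other items in the same list are fixed at or before entry: "Systolic blood pressure <90 mmHg or mean arterial pressure <65 mmHg at the moment of admission", "Use of renal replacement therapy or ultrafiltration before study inclusion", and a limit on prior loop-diuretic dose that counts treatment "during the index hospitalization before randomization". The item on nephrotoxic exposure looks forward but asks only what is anticipated, which can be judged at enrolment.

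The plan does not define when the study ends. The acetazolamide primary endpoint is "Total urinary sodium excretion (mmol) after 24 h" (3.5.1). The spironolactone primary endpoint counts potassium events "during the entire 72 h interval after randomization" (3.5.2). Contact continues well beyond both: "The patient will receive a telephone call from a study nurse after 3, 6, 9 and 12 months" (3.4).

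Section 3.6 covers summaries, the normality check, tests, significance level and software. It compares groups without naming an analysis set, and no other section names one. The only rule for a post-randomisation event is the censoring of therapy-refractory patients in 3.3.1 and 3.3.2, which does not mention these drugs.

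**The concern.** An eligibility rule should depend only on what is known before allocation. This one depends in part on what happens afterwards. The diuretic regimens differ between groups, and a patient's haemodynamic course may respond to them, so use of these drugs could be a consequence of treatment. If such patients leave the analysis, membership of the compared groups is no longer settled by randomisation alone.

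The window makes this sharper. A patient with a complete 24 h sodium collection could be excluded for drug use on day 3 or, on the widest reading, months later. Because the plan does not require removals to be reported by group, a reader could not tell whether this had happened or in which direction it acted.

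**Working it through.** **Text.** The claim rests on two readings, and both hold. The window extends past randomisation, since neighbouring items carry explicit pre-entry limits and this one does not. No section names an intention-to-treat, per-protocol or other set, or gives a rule for a patient who meets an exclusion after allocation.

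**Inputs for scale.** From 3.1: four groups of 20, so each factor compares 20 + 20 = 40 v 40. From 3.6: two-sided 0.05. The sample size cannot be reproduced, because the plan states no power, effect size, SD or event rate. Removal rates, correlations and the 80% power are therefore assumptions.

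**Detectable difference.** Normal approximation: (1.960 + 0.842) × √(2/40) = 0.626 SD. With the t distribution it is 0.634 SD, so 0.63 SD either way.

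**Bias in 24 h natriuresis, no true effect.** Suppose a fraction p of a group is removed from the lower tail of a latent score that has correlation ρ with the outcome. The mean of those left rises by ρ·φ(c)/(1 − p) SD, where c is the p-quantile of the standard normal. At p = 0.05 the factor is 0.1031/0.95 = 0.1086; at p = 0.10 it is 0.1755/0.90 = 0.1950. The bias is the difference between groups. For example, at ρ = 0.5, 5% v 0% gives 0.5 × 0.1086 = 0.054 SD, and 10% v 5% gives 0.5 × (0.1950 − 0.1086) = 0.043 SD. The simulation used 40,000 replicates per row, with removal by threshold:

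| Removal (expected patients) | ρ | Bias, formula | Bias, simulated | t-test type I | Mann–Whitney type I |
|---|---|---|---|---|---|
| 5% v 0% (2 v 0) | 0.5 | 0.054 | 0.054 | 5.7% | 5.5% |
| | 0.7 | 0.076 | 0.076 | 6.1% | 5.9% |
| 10% v 5% (4 v 2) | 0.5 | 0.043 | 0.042 | 5.3% | 5.3% |
| | 0.7 | 0.061 | 0.059 | 5.7% | 5.7% |
| 10% v 0% (4 v 0) | 0.5 | 0.097 | 0.098 | 7.2% | 6.8% |
| | 0.7 | 0.136 | 0.139 | 9.0% | 8.6% |
| 10% v 10% (4 v 4) | 0.5 | 0 | 0.00 | 5.0% | 4.9% |
| | 0.7 | 0 | 0.00 | 4.9% | 4.9% |

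Patient counts are expected numbers. Removing exactly 4 v 2 gives a t-test error of 5.8% to 6.9% at these correlations. With ρ = 0 there is no bias. With ρ = 0.2 the bias is 0.02 to 0.04 SD and the error about 4.9% to 5.5%. Equal removal with unequal correlation (0.7 v 0.5) gives 0.2 × 0.1086 = 0.022 SD at 5% and 0.2 × 0.1950 = 0.039 SD at 10%.

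**Potassium endpoint.** Let the true incidence be π, overall removal p, and removal r times as likely after an event. Then the removal probability is p/(1 − π + rπ) without an event and r times that with one. The incidence among those left is π(1 − removal probability with an event)/(1 − p). Two cases mark the ends of the range:

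- π = 20%, r = 2, 5% v 0%: 0.20 × (1 − 0.0833)/0.95 = 19.30%, a bias of 0.70 percentage points.
- π = 30%, r = 3, 10% v 0%: 0.30 × (1 − 0.1875)/0.90 = 27.08%, a bias of 2.92 points.

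Across π of 20%, 30% and 50%, r of 2 and 3, and the three unequal removal patterns, Fisher's exact test has a type I error of 3.3% to 4.3% (20,000 replicates), against 2.6% to 3.2% with no removal.

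**Precision.** Losing 10% from each side (36 v 36) lowers power at 0.63 SD from 80% to 76%.

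**The case against.** The strongest reply is that the harm needs a step the plan never states. An exclusion criterion governs entry. Where this protocol wants later results to stop counting, in the therapy-refractory rule of 3.3.1 and 3.3.2, it says so, and it says nothing of the kind for these drugs. The item may simply be a misplaced restriction on concomitant treatment. Section 3.1 defines the groups by allocation, so the natural reading of 3.6 is a comparison as allocated. The study may also mean only the treatment phase of about 72 h, in which case the window does not outlast the potassium endpoint. The bias figures are wholly assumed, and mostly small.

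Much of this is fair. Removal is permitted rather than prescribed, and the 12-month reach is only the widest reading. Even on the narrow reading, though, the window outlasts the 24 h endpoint. The contrast with the censoring rule supports the benign interpretation but does not prove it. With no stated analysis set, the choice could be made after the data are seen.

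Two features lower the risk: low blood pressure at admission is an exclusion, and the treating physician and investigator are blinded in both arms. Neither prevents a difference produced by the treatments themselves.

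The gap is also wider than this one item. The exclusion for diuretics or mineralocorticoid receptor antagonists outside the protocol has no time limit either.

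**Conclusion.** The concern holds. As written, the criterion allows randomised patients to be excluded for a post-allocation event, and nothing in the plan keeps them in. That conclusion rests on the text and not on the simulations.

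The likely size is modest. Bias in 24 h natriuresis is 0.04 to 0.14 SD, and the t-test error is 5.3% to 9.0%, only if removal is unequal and correlated 0.5 to 0.7 with outcome. The bias vanishes when removal is unrelated to outcome, or when both removal and correlation are equal between groups. The potassium comparison keeps its error below 5%, although its estimate can shift by 0.7 to 2.9 percentage points. The point should be fixed, but it is not a fatal flaw.

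**What to change.** 1. In 3.2.2, limit this criterion, as an eligibility rule, to information available before randomisation.
2. Add to 3.6: *All randomised patients are analysed in the group to which they were allocated. Use of an intravenous inotrope, vasopressor or nitroprusside between randomisation and 72 h is recorded, reported by group, and does not by itself remove the patient from the analysis.*

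The 72 h window matches the potassium endpoint. The first sentence also keeps in patients with later use, and it covers the other open-ended item on diuretics and mineralocorticoid receptor antagonists. An analysis without users of these drugs can be kept as a sensitivity analysis. The authors should reconcile the new text with the censoring wording in 3.3.1 and 3.3.2, which is a separate matter. None of this affects when clinicians use these drugs.

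The cost is one reworded criterion and two sentences. The small downside is that some analysed patients will have received these drugs.

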3.3. Interventions (See Addendum 1 for therapy schedules)

3.3.1. Arm 1, control group: High-dose loop diuretics

- At the moment of randomization the patient receives an intravenous bolus of loop diuretics at a dose equal to the double of his normal daily oral dose (e.g. a patient who takes 1x1 mg bumetanide will receive 2x1x1 mg = 2mg; or a patient who takes 2x1 mg bumetanide will receive 2x2x1 mg = 4mg).
- The next three days, the patient will receive the same dose equally divided between two administrations at 10u00 and 16u00 provided that the treating physician has concluded during the morning rounds that the patient is still volume overloaded.
- If diuresis since administration of the previous dose of loop diuretics is <1,500 mL and the patient is still volume overload, subsequent bolus doses are doubled.
- If after doubling of the dose, the patient is considered therapy-refractory. The treating physician is recommended to add chlorthalidone 50mg once daily and consider ultrafiltration or renal replacement therapy after which results of the patient will be censored.
- Switch to treatment at the discretion of the treating physician if any of the following criteria is fulfilled
 - After 3 days
 - The patient had no longer clinical signs or symptoms of congestion
 - Doubling of the serum creatinine value

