MRA have an established role in the treatment of chronic CHF.^{11, 12} However there are remarkable few data on their use in patients who present with ADHF. Nevertheless, in this context with frequent use of potassium wasting diuretics, they might be of particular interest to prevent occurrence of hypokalemia, which has been associated with a worse prognosis.²⁷ Moreover, by inhibiting distal tubular sodium reabsorption and counteracting aldosterone breakthrough, MRA might improve the natriuretic efficiency of loop diuretics.

2. Study Hypotheses

1. Combination therapy with acetazolamide improves loop diuretic efficacy to induce natriuresis in ADHF patients, allowing for a lower dose of the latter medication and potentially less adverse events such as worsening renal function.
2. Combination therapy with acetazolamide and low-dose loop diuretics leads to less pronounced neurohumoral activation compared to treatment with high-dose loop diuretics in ADHF patients.
3. Upfront therapy with MRA is safe in patients presenting with ADHF and lowers the incidence of hypokalemia and the need for potassium supplementation, without causing a higher incidence of hyperkalemia.
4. Combination diuretic therapy with acetazolamide and/or upfront spironolactone will lead to improved clinical outcome (less heart failure rehospitalizations and lower all-cause mortality).

3. Study Protocol

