3.3.2. Arm 1, treatment group: Acetazolamide + low-dose loop diuretics

- At the moment of randomization, the patient receives 500 mg of intravenous acetazolamide and 2 mg of intravenous bumetanide in bolus.
- The next three days, the patient will receive 250 mg of intravenous acetazolamide and 1 mg of intravenous bumetanide in bolus at 10u00 provided that the treating physician has concluded during the morning rounds that the patient is still volume overloaded.

- If diuresis since administration of the previous dose of loop diuretics is <1,500 mL and the patient is still volume overloaded, the patient continues to receive 500 mg of acetazolamide and 2 mg of bumetanide.
- If after doubling of the dose, the patient is considered therapy-refractory. The treating physician is recommended to add chlorthalidone 50mg once daily and consider ultrafiltration or renal replacement therapy after which results of the patient will be censored.
- Switch to treatment at the discretion of the treating physician if any of the following criteria is fulfilled
 - After 3 days
 - The patient had no longer clinical signs or symptoms of congestion
 - Doubling of the serum creatinine value

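### Section 3.6 neither adjusts the 24 h sodium comparison for home loop dose nor shows the effect by it, although both Arm 1 groups get the same 2 mg first bolus at the minimum home dose

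*Combined protocol and SAP*

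**What the plan says.** Section 3.1 declares the Arm 1 contrast as "Acetazolamide + low-dose loop diuretics versus high-dose loop diuretics (=standard of care". Section 3.2.1 admits patients on "Maintenance therapy with oral loop diuretics at a dose of at least 1 mg bumetanide or an equivalent dose".

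In the control group (3.3.1) the first bolus is double the home dose, with the worked example "a patient who takes 1x1 mg bumetanide will receive 2x1x1 mg = 2mg". On the following three days the patient gets "the same dose equally divided between two administrations at 10u00 and 16u00". In the acetazolamide group (3.3.2) "the patient receives 500 mg of intravenous acetazolamide and 2 mg of intravenous bumetanide in bolus", whatever the home dose, followed by "250 mg of intravenous acetazolamide and 1 mg of intravenous bumetanide in bolus at 10u00". Both groups have a doubling rule when diuresis stays below 1,500 mL.

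The Arm 1 primary end-point (3.5.1) is "Total urinary sodium excretion (mmol) after 24 h", and 3.4 starts the urine collection at the first loop bolus. Hypothesis 1 in section 2 says that acetazolamide "improves loop diuretic efficacy to induce natriuresis in ADHF patients, allowing for a lower dose of the latter medication".

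For continuous outcomes, section 3.6 gives a Student's t-test or a Mann-Whitney test after a normality check. It names no covariate, subgroup or model. Section 3.1 describes blocks of 4 and mentions no stratification by home dose.

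**The concern.** Home dose sets the size of the loop-dose contrast between the two Arm 1 groups. At 1 mg the first bolus tests acetazolamide added to an equal loop dose. Above 1 mg it tests acetazolamide plus a smaller loop dose against a larger one. Hypothesis 1 covers both ideas, better natriuresis and room for a lower loop dose. At the first bolus, only patients above 1 mg bear on the second.

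A single pooled 24 h figure does not show how much of the effect comes from patients whose loop dose was lower in that window. Home dose may also predict sodium excretion. If it does, leaving it out of the analysis gives up precision in a trial of 40 v 40.

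**Working it through.** **Inputs.** Home dose D (mg bumetanide per day, at least 1; section 3.2.1 gives the conversion from furosemide and torsemide). Control (3.3.1): first bolus 2D, then D at 10:00 and D at 16:00. Treated (3.3.2): first bolus 2 mg, then 1 mg at 10:00. Sample size (3.1): 4 × 20 = 80, so 40 v 40 for Arm 1. The plan states no effect size, SD or power, so its sample size cannot be reproduced. Effects below are in SD units.

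**First bolus.** The plan's own examples reproduce: 2 × 1 = 2 mg and 2 × 2 = 4 mg.

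**Planned loop dose in the 24 h window.** This assumes that the first of the next three days is the calendar day after randomization, that the patient is still overloaded, and that no dose is escalated. Randomized before 10:00, no later dose falls in the window: 2D v 2. Between 10:00 and 16:00, one does: 2D + D = 3D v 2 + 1 = 3. After 16:00, both control doses do: 2D + 2D = 4D v 3.

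| Home dose | First bolus | Before 10:00 | 10:00–16:00 | After 16:00 |
|---|---|---|---|---|
| 1 mg | 2 v 2 | 2 v 2 | 3 v 3 | 4 v 3 |
| 2 mg | 4 v 2 | 4 v 2 | 6 v 3 | 8 v 3 |
| 4 mg | 8 v 2 | 8 v 2 | 12 v 3 | 16 v 3 |

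So at 1 mg the reduction is 0, 0 or 1 mg. With escalation at 1 mg:

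- both groups escalate: 4 v 4 (10:00–16:00) or 6 v 4 (after 16:00);
- only control escalates: 4 v 3 or 6 v 3.

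Over the full course without escalation the totals are 2D + 3 × 2D = 8D v 2 + 3 × 1 = 5 mg, that is 8 v 5 at 1 mg.

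**Why the mix matters.** Suppose, purely for illustration, an effect of 0.8 SD at 1 mg and 0.2 SD above. With 25%, 50% or 75% of patients at 1 mg the pooled effect is 0.25 × 0.8 + 0.75 × 0.2 = 0.35, then 0.50, then 0.65 SD.

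**Adjustment, normal outcome.** 8,000 simulated trials per setting, 40 v 40, assumed mix 50% at 1 mg, 25% at 2 mg and 25% at 4 mg, within-dose SD 1, same slope in both groups:

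| Slope per doubling | SE, unadjusted v adjusted | Power at 0.6 SD |
|---|---|---|
| 0 | 0.224 v 0.226 | 76 v 76% |
| −0.25 SD | 0.228 v 0.225 | 74 v 75% |
| −0.5 SD | 0.242 v 0.226 | 70 v 76% |

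Type I error of the adjusted model was 4.5–5.5% across slopes and mixes. If slopes differ by group the gain shrinks: with 0 (control) and −0.5 (treated), power is 71 v 73%; with +0.25 and −0.25 it is 74 v 74%.

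**Adjustment, skewed outcome.** With log-normal errors (log-SD 0.7) and slope −0.25, also assumed:

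| Effect | Linear model, untransformed | Mann-Whitney | Same covariate, on ranks |
|---|---|---|---|
| Shift | 76% | 95% | 96% |
| Multiplicative | 65% | 70% | 72% |

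The rank model's type I error was about 5%.

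**Chance imbalance.** By the hypergeometric distribution, the groups differ by 6 or more 1 mg patients with probability 26% if 40 of 80 are at 1 mg, and 20% if 20 or 60 are.

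**Precision by home dose.** The 95% CI half-width t(0.975, n−2) × √(4/n) is 0.94, 0.64 and 0.52 SD for 20, 40 and 60 patients, against 0.45 for all 80. An interaction test would have 16–20% power for a 0.5 SD difference between subgroups if 25–75% of patients are at 1 mg.

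**The case against.** The strongest objection is that nothing here is an error. Section 3.1 declares a strategy contrast and the planned test estimates it. Randomization protects it, and chance imbalance in home dose is already covered by the test's error rate. All of that stands. A reader might infer that the pooled test is biased or that the trial cannot answer its question; the documents do not support either.

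A reader might also infer that the plan intends to claim dose-sparing from the 24 h result. It does not: 3.5.1 measures sodium only, and over the full course even a 1 mg patient on acetazolamide is scheduled for less loop diuretic (8 v 5 mg).

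Two further objections shape the fix. First, adjustment does not separate the add-on question from the dose question, because it still estimates one pooled effect; only the by-dose lines speak to that. Second, replacing the planned rule with a linear model on untransformed sodium would lose power if sodium is skewed, because the plan already turns to Mann-Whitney in that case. A rank version with the same covariate avoids the loss in the settings tried. The model should also carry Arm 2 allocation, the other randomized factor.

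Finally, the window doses are no-escalation figures, and Addendum 1, which holds the therapy schedules, is not in the text available for this review. The equal first bolus does not depend on either.

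**Conclusion.** The point holds as an optional improvement, with medium confidence. The equality of first boluses at 1 mg and the lack of any home-dose adjustment or display in 3.6 are plain from the text. The precision gain is 0 to about 6 points of power at 0.6 SD under the assumed slopes and mix, and smaller if slopes differ by group.

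The interpretive part has unknown size, because the documents give neither the share of patients at 1 mg nor the effect by home dose. If nobody enters at 1 mg, the equal-bolus issue vanishes. The point is confined to the 24 h end-point and puts no limit on conclusions from the 48 h, 72 h or renal results.

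**What to change.** Add to section 3.6, fixed before unblinding:

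> The Arm 1 primary analysis of 24 h urinary sodium adjusts for baseline home loop dose (log2 mg bumetanide equivalent per day) and Arm 2 allocation: a linear model where the planned normality check supports the t-test, and the same model on ranks where it would lead to Mann-Whitney. The unadjusted t-test or Mann-Whitney test is a sensitivity analysis. The Arm 1 effect on 24 h sodium is also reported descriptively, with 95% CI, for home dose 1 mg and >1 mg.

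**Cost of the adjustment.** No new data: control dosing already requires the home dose, and 3.4 records current therapy at baseline. If home dose is not prognostic, the CI half-width goes from 0.443 to 0.446 SD (0.446/0.443 = 1.007). Arm 2 allocation takes one more degree of freedom. The rank model gives a test but no effect in mmol, so the group difference in mmol has to be reported beside it.

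**Cost of the by-dose lines.** Analysis work only. The intervals are wide and the contrast between subgroups is not randomized. The >1 mg group mixes 4 v 2 with 8 v 2 boluses and combines add-on with dose reduction. It therefore shows the strategy effect where the loop dose was lower, not a pure dose effect, and should not be tested.
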